Appendix 12: Study Details Specific to RO7247669 2100 mg Arm

The supporting data for the selected dose can be found in the RO7247669 Investigator's Brochure.

A12-4 MATERIALS AND METHODS SPECIFIC TO RO7247669 2100 mg ARM

A12-4.1 TREATMENT IN RO7247669 2100 mg ARM

A12-4.1.1 Formulation, Packaging, and Handling

The RO7247669 drug product will be supplied by the Sponsor as a 50 mg/mL concentrate for solution for infusion.

For information on the formulation, packaging, and handling of RO7247669, refer to the pharmacy manual and the RO7247669 Investigator's Brochure.

A12-4.1.2 Dosage, Administration, and Compliance

Patients in the RO7247669 2100 mg arm will receive treatment for 2 cycles (6 weeks) as outlined in [Table A12-1](#) until surgery, or until unacceptable toxicity or loss of clinical benefit, whichever occurs first (see Section [3.1.2](#) for details). It is recommended that treatment be initiated no later than 7 days after randomization.

Table A12-1 Treatment Regimen for RO7247669 2100 mg Arm

Cycle Length	Dose, Route, and Regimen
21 days	
• RO7247669 2100 mg by IV infusion on Day 1 of each cycle

Refer to the pharmacy manual for detailed instructions on drug preparation, storage, and administration.

Medication errors should be noted on the Study Drug Administration electronic Case Report Form (eCRF). Cases of accidental overdose or medication error, along with any associated adverse events, should be reported as described in Section [5.3.5.12](#). No safety data related to overdosing of RO7247669 are available to date.

RO7247669 will be administered by IV infusion at a fixed dose of 2100 mg on Day 1 of each 21-day cycle.

Administration of RO7247669 will be performed in a monitored setting where there is immediate access to trained personnel and adequate equipment and medicine to manage potentially serious reactions. For anaphylaxis precautions, see [Appendix 8](#). RO7247669 infusions will be administered per the instructions outlined in [Table A12-2](#).

Appendix 12: Study Details Specific to RO7247669 2100 mg Arm

Table A12-2 Administration of First and Second RO7247669 Infusions

First Infusion	Second Infusion

• No premedication is permitted prior to the first RO7247669 infusion.• Vital signs (pulse rate, respiratory rate, blood pressure, pulse oximetry, and temperature) should be measured within 60 minutes prior to the infusion and recorded on the eCRF.• RO7247669 should be infused over 60 (± 10) minutes.• After the infusion of RO7247669, the patient begins a 60-minute observation period.• If clinically indicated, vital signs should be measured every 15 (± 5) minutes during the infusion and at 30 (± 10) minutes after the infusion. Record on the eCRF in case of abnormalities.• Patients should be informed about the possibility of delayed post-infusion symptoms and instructed to contact their study physician if they develop such symptoms.	
• If the patient experienced an IRR with the first infusion, premedication with antihistamines, antipyretics, and/or analgesics may be administered for subsequent doses at the discretion of the investigator.• Vital signs should be measured within 60 minutes prior to the infusion and recorded on the eCRF.• RO7247669 should be infused over 30 (± 10) minutes if the first infusion was tolerated without an IRR, followed by a 30-minute observation period.• If the patient experienced an IRR with the previous infusion or if clinically indicated, vital signs should be measured every 15 (± 5) minutes during the infusion and at 30 (± 10) minutes after the infusion. Record on the eCRF in case of abnormalities.

eCRF = electronic Case Report Form; IRR = infusion-related reaction.

For patients who experience a Grade 2 infusion-related reaction (IRR), premedication with paracetamol 500–1000 mg orally [PO] or IV and diphenhydramine 25–50 mg PO or IV (or an alternative histamine H_{1/2} antagonist at an adequate dose) is required prior to subsequent infusions. In case of Grade 3 or 4 IRRs related to study treatment, the patient should be permanently discontinued from the study treatment.

Guidelines for medical management of IRRs for RO7247669 are provided in Section [A12–5.1.2.3](#).

No dose modification for RO7247669 is allowed. Guidelines for treatment interruption or discontinuation because of toxicities are provided in Section [A12–5.1.2.2](#).

Appendix 12: Study Details Specific to RO7247669 2100 mg Arm

A12–4.2 CONCOMITANT THERAPY FOR RO7247669 2100 mg ARM

Concomitant therapy consists of any medication (e.g., prescription drugs, over-the-counter drugs, vaccines, herbal or homeopathic remedies, nutritional supplements) used by a patient in addition to protocol-mandated study treatment from 7 days prior to initiation of study treatment to the treatment discontinuation visit. All such medications should be reported to the investigator and recorded on the Concomitant Medications eCRF.

A12–4.2.1 Permitted Therapy for RO7247669 2100 mg Arm

Patients are permitted to use the following therapies during the study:

- Oral contraceptives with a failure rate of <1% per year
- Hormone-replacement therapy
- Prophylactic or therapeutic anticoagulation therapy (such as warfarin at a stable dose or low-molecular-weight heparin)
- Vaccinations (such as influenza, COVID-19)

Live, attenuated vaccines are not permitted (see Section [A12–4.2.3](#))

- Megestrol acetate administered as an appetite stimulant
- Mineralocorticoids (e.g., fludrocortisone)
- Corticosteroids administered for chronic obstructive pulmonary disease or asthma
- Low-dose corticosteroids administered for orthostatic hypotension or adrenocortical insufficiency. Other use of corticosteroids may be at the investigator's discretion. The Medical Monitor is available to advise as needed.
- Local therapy (e.g., surgery other than complete lymph node dissection [CLND] that is not considered to be related to melanoma)

Premedication with antihistamines, antipyretics, and/or analgesics may be administered for the second RO7247669 infusion only, at the discretion of the investigator.

In general, investigators should manage a patient's care (including preexisting conditions) with supportive therapies other than those defined as cautionary or prohibited therapies as clinically indicated, per local standard practice. Patients who experience infusion-associated symptoms may be treated symptomatically with acetaminophen, ibuprofen, diphenhydramine, and/or H_{1/2}-receptor antagonists (e.g., famotidine, cimetidine), or equivalent medications per local standard practice. Serious infusion-associated events manifested by dyspnea, hypotension, wheezing, bronchospasm, tachycardia, reduced oxygen saturation, or respiratory distress should be managed with supportive therapies as clinically indicated (e.g., supplemental oxygen and β₂-adrenergic agonists; see [Appendix 8](#)).

Appendix 12: Study Details Specific to RO7247669 2100 mg Arm

A12–4.2.2 Cautionary Therapy for RO7247669 2100 mg Arm

A12–4.2.2.1 Corticosteroids, Immunosuppressive Medications, and Tumor Necrosis Factor- α Inhibitors

Systemic corticosteroids, immunosuppressive medications, and tumor necrosis factor (TNF)- α inhibitors may attenuate potential beneficial immunologic effects of treatment with RO7247669. Therefore, in situations in which systemic corticosteroids, immunosuppressive medications, or TNF- α inhibitors would be routinely administered, alternatives, including antihistamines, should be considered. If the alternatives are not feasible, systemic corticosteroids, immunosuppressive medications, and TNF- α inhibitors may be administered at the discretion of the investigator.

Systemic corticosteroids or immunosuppressive medications are recommended, at the discretion of the investigator, for the treatment of specific adverse events when associated with RO7247669 therapy (see [Appendix 9](#) for details).

A12–4.2.2.2 Herbal Therapies

Concomitant use of herbal therapies is not recommended because their pharmacokinetics, safety profiles, and potential drug–drug interactions are generally unknown. However, herbal therapies not intended for the treatment of cancer (see Section [A12–4.2.3](#)) may be used during the study at the discretion of the investigator.

A12–4.2.3 Prohibited Therapy for RO7247669 2100 mg Arm

Use of the following concomitant therapies is prohibited as described below:

- Concomitant therapy intended for the treatment of cancer (including, but not limited to, chemotherapy, hormonal therapy, immunotherapy, radiotherapy, and herbal therapy), whether health authority–approved or experimental, is prohibited for various time periods prior to starting study treatment, depending on the agent (see Section [4.1.2](#)), and during study treatment until surgery or, if earlier, disease progression is documented and the patient has discontinued study treatment.
- Investigational therapy is prohibited within 28 days prior to initiation of study treatment and during study treatment.
- Live, attenuated vaccines (e.g., FluMist[®]) are prohibited within 4 weeks prior to initiation of study treatment, during treatment with RO7247669, and for 4 months after the final dose of RO7247669.
- Systemic immunostimulatory agents (including, but not limited to, interferons and interleukin-2) are prohibited within 4 weeks or 5 drug-elimination half-lives (whichever is longer) prior to initiation of study treatment and during study treatment because these agents could potentially increase the risk for autoimmune conditions when given in combination with RO7247669.

Appendix 12: Study Details Specific to RO7247669 2100 mg Arm

A12–4.3 CONTRACEPTION REQUIREMENTS FOR RO7247669 2100 mg ARM

Contraception requirements for women and men in the RO7247669 2100 mg arm are outlined below:

- For women of childbearing potential: agreement to remain abstinent (refrain from heterosexual intercourse) or use contraception, as defined below:

Women must remain abstinent or use contraceptive methods with a failure rate of < 1% per year during the treatment period and for 4 months after the final dose of RO7247669.

A woman is considered to be of childbearing potential if she is postmenarcheal, has not reached a postmenopausal state (≥ 12 continuous months of amenorrhea with no identified cause other than menopause), and is not permanently infertile due to surgery (i.e., removal of ovaries, fallopian tubes, and/or uterus) or another cause as determined by the investigator (e.g., Müllerian agenesis). The definition of childbearing potential may be adapted for alignment with local guidelines or regulations.

Examples of contraceptive methods with a failure rate of < 1% per year include bilateral tubal ligation, male sterilization, hormonal contraceptives that inhibit ovulation, hormone-releasing intrauterine devices, and copper intrauterine devices.

The reliability of sexual abstinence should be evaluated in relation to the duration of the clinical trial and the preferred and usual lifestyle of the patient. Periodic abstinence (e.g., calendar, ovulation, symptothermal, or postovulation methods) and withdrawal are not acceptable methods of contraception.

If required per local guidelines or regulations, locally recognized acceptable methods of contraception and information about the reliability of abstinence will be described in the local Informed Consent Form.

- For men: agreement to remain abstinent (refrain from heterosexual intercourse) or use contraception, and agreement to refrain from donating sperm, as defined below:

With a female partner of childbearing potential who is not pregnant or a pregnant female partner, men who are not surgically sterile must remain abstinent or use a condom plus an additional contraceptive method that together result in a failure rate of < 1% per year during the treatment period, for 4 months after the last dose of RO7247669 to avoid exposing the embryo. Men must refrain from donating sperm during this same period.

Appendix 12: Study Details Specific to RO7247669 2100 mg Arm

The reliability of sexual abstinence should be evaluated in relation to the duration of the clinical trial and the preferred and usual lifestyle of the patient. Periodic abstinence (e.g., calendar, ovulation, symptothermal, or postovulation methods) and withdrawal are not acceptable methods of preventing drug exposure. If required per local guidelines or regulations, information about the reliability of abstinence will be described in the local Informed Consent Form.

A12–5 ASSESSMENT OF SAFETY FOR RO7247669 2100 mg ARM

A12–5.1 SAFETY PLAN FOR RO7247669 2100 mg ARM

The safety plan for patients in this study is based on clinical experience with RO7247669 in ongoing studies. The potential safety risks are outlined below (see Section [A12–5.1.1](#)). Guidelines for management of patients who experience specific adverse events are provided in Section [A12–5.1.2](#) and [Appendix 9](#).

Measures will be taken to ensure the safety of patients participating in this study, including the use of stringent inclusion and exclusion criteria and close monitoring of patients during the study. Special caution will be taken by performing a planned safety evaluation phase for patients randomized to this arm (see Section [3.1.3](#)).

Administration of study treatment will be performed in a monitored setting in which there is immediate access to trained personnel and adequate equipment and medicine to manage potentially serious reactions. Adverse events will be reported as described in Sections [5.2–5.6](#).

A12–5.1.1 Risks Associated with RO7247669

Clinical evaluation of RO7247669 is ongoing, and not all risks are known. As an antagonist of PD-1 and LAG-3, RO7247669 is anticipated to enhance T-cell and NK-cell proliferation, survival, and function. Based on the mechanism-of-action of RO7247669, the safety profile is anticipated to be similar to other CPIs. Potential risks associated with RO7247669 include the following: IRRs (including anaphylaxis), immunogenicity, and immune-mediated adverse events. Refer to Section 6 of the RO7247669 Investigator's Brochure for a detailed description of anticipated safety risks for RO7247669.

A12–5.1.1.1 Infusion-Related Reactions and Anaphylaxis

Administration of therapeutic antibodies may cause IRRs, which may include symptoms such as fever, chills, hypotension, shortness of breath, skin rash, headache, nausea, and vomiting. Such reactions typically occur during or shortly after the infusion and are predominantly reported following the first infusion. The incidence and severity of IRRs typically decrease with subsequent infusions. Based on in vitro data, the risk of proinflammatory cytokine-mediated IRRs on first administration of RO7247669 as a single agent is considered low.

Appendix 12: Study Details Specific to RO7247669 2100 mg Arm

Refer to Section [A12–4.1.2](#) for detailed guidance on administration of RO7247669 in this study. Refer to [Appendix 8](#) for guidance on anaphylaxis precautions and to Section [A12–5.1.2.3](#) for guidance on the management of IRRs.

A12–5.1.1.2 Immunogenicity

Administration of therapeutic antibodies may cause the formation of anti-drug antibodies, which may negatively affect the safety of the therapeutic (e.g., allergic reactions, immune complex-mediated diseases).

A12–5.1.1.3 Immune-Mediated Adverse Events

The co-stimulatory action of RO7247669, in particular its effects on LAG-3, may lead to an exaggerated risk of immune cell activation that may result in the occurrence of enhanced, untoward, immune-mediated adverse events and increased cytokine release-mediated toxicities.

Toxicities from PD-1 blocking agents can involve any organ or tissue, although some immune-mediated adverse events occur much more frequently than others. The most frequently occurring immune-mediated adverse events affect skin, colon, endocrine organs, liver, and lungs. Others are very infrequent but may be very serious, even lethal, such as neurological disorders and myocarditis.

The limited data from recent early phase studies showed anti-LAG-3 therapy was generally well tolerated as a monotherapy or in combination with anti-PD-1 therapies, and data were consistent with the safety profiles of other CPIs (Ascierto et al. 2017; Hong et al. 2018).

In this study, specified immune-mediated adverse events will be considered adverse events of special interest and will be captured accordingly (see Section [A12–5.2](#) for the list of adverse events of special interest and Section [5.4.2](#) for reporting instructions).

Patients with a history of autoimmune disease will be excluded from this study. Please see Section [4.1.2](#) for details.

A12–5.1.2 Management of Patients Who Experience Specific Adverse Events in RO7247669 2100 mg Arm

A12–5.1.2.1 Dose Modifications

There will be no dose modifications for RO7247669 in this study.

A12–5.1.2.2 Treatment Interruption for Toxicities

RO7247669 treatment may be temporarily suspended in patients experiencing toxicity considered to be related to study treatment. If corticosteroids are initiated for treatment of the toxicity, they must be tapered over ≥ 1 month to ≤ 10 mg/day oral prednisone or equivalent before RO7247669 can be resumed if warranted. In the neoadjuvant setting,

Appendix 12: Study Details Specific to RO7247669 2100 mg Arm

the study treatment is limited to a pre-surgery window of 6 weeks. Treatment during this period should not be interrupted, unless a patient experiences toxicity. If toxicity meets criteria for interrupting/withholding RO7247669, RO7247669 should be interrupted/withheld. After resolution of the toxicity, subsequent treatment cycles should only be considered if the benefit-risk profile is acceptable and if the surgery can be conducted within 2 weeks of the planned date. Otherwise, subsequent treatment cycles should be omitted to allow the patient to proceed directly to surgery without further delay.

A12–5.1.2.3 Management Guidelines for Adverse Events

Guidelines for management of patients who experience specific adverse events are provided in [Table A12-3](#).

Appendix 12: Study Details Specific to RO7247669 2100 mg Arm

Table A12-3 Guidelines for Management of Patients Who Experience Adverse Events in RO7247669 2100 mg Arm

Event	Action to Be Taken
IRRs, anaphylaxis, and hypersensitivity reactions	
General guidance	
For anaphylaxis precautions, see Appendix 8.For severe hypersensitivity reactions, permanently discontinue RO7247669.For suspected CRS, see Appendix 9 for guidance on supportive care.Determine tryptase concentration and IgE titer if clinical presentation of IRR suggests an anaphylactic or hypersensitivity reaction (hives, obstructive shortness of breath, urticaria, other histamine associated symptoms) and/or if the first IRR or CRS (\geqGrade 2) is observed at the second infusion. If tryptase and/or IgE are elevated, collect a second sample for IgE/trypase analysis at least 48 hours after the onset of the reaction to rule out the possibility of an anaphylactic reaction.
IRR to RO7247669, Grade 1 or 2	
Slow infusion to \leq50% or interrupt infusion.Give supportive treatment. Patients should be treated with acetaminophen/paracetamol and an antihistamine, such as diphenhydramine, if they have not been administered in the last 4 hours. IV fluids (e.g., normal saline) may be administered as clinically indicated. For bronchospasm, urticaria, or dyspnea, antihistamines, oxygen, corticosteroids (e.g., 100 mg IV prednisolone or equivalent), and/or bronchodilators may be administered per institutional practice.Upon symptom resolution, infusion may resume (if interrupted) at 50% starting rate. The infusion must remain at the lower rate resulting in symptom resolution for the remainder of the infusion.For Grade 2 IRRs, subsequent doses of RO7247669 should be administered with pre-medication, including acetaminophen/paracetamol and an antihistamine such as diphenhydramine.For Grade 2 wheezing or urticaria, patient must also be pre-medicated prior to subsequent doses (as described above).If symptoms recur with the same or greater severity following the slower or interrupted infusion, the infusion must be stopped immediately. No further RO7247669 will be administered for the cycle.

CRS=cytokine-release syndrome; GI=gastrointestinal; HLH=hemophagocytic lymphohistiocytosis; IRR=infusion-related reaction; MAS=macrophage activation syndrome.

Appendix 12: Study Details Specific to RO7247669 2100 mg Arm

Table A12-3 Guidelines for Management of Patients Who Experience Adverse Events in RO7247669 2100 mg Arm (cont.)

Event	Action to Be Taken
IRR to RO7247669, Grade 3–4	
• Discontinue infusion immediately.• Give supportive treatment.• Permanently discontinue study treatment.
Pulmonary, hepatic, GI, endocrine, ocular, immune-mediated myocarditis, CRS, pancreatic, dermatologic, neurologic, immune-mediated meningoencephalitis, renal, myositis, HLH, MAS, and systemic immune activation	
• Guidelines for the management of these events are provided in Appendix 9.

CRS=cytokine-release syndrome; GI=gastrointestinal; HLH=hemophagocytic lymphohistiocytosis; IRR=infusion-related reaction; MAS=macrophage activation syndrome.

Appendix 12: Study Details Specific to RO7247669 2100 mg Arm

A12–5.2 ADVERSE EVENTS OF SPECIAL INTEREST FOR RO7247669 2100 mg ARM (IMMEDIATELY REPORTABLE TO THE SPONSOR)

Adverse events of special interest are required to be reported by the investigator to the Sponsor immediately (i.e., no more than 24 hours after learning of the event; see Section 5.2.3 for reporting instructions). Adverse events of special interest for the RO7247669 2100 mg arm are as follows:

- Cases of potential drug-induced liver injury that include an elevated ALT or AST in combination with either elevated bilirubin or clinical jaundice, as defined by Hy's Law (see Section 5.3.5.7)
- Suspected transmission of an infectious agent by the study treatment, as defined below:

Any organism, virus, or infectious particle (e.g., prion protein transmitting transmissible spongiform encephalopathy), pathogenic or non-pathogenic, is considered an infectious agent. A transmission of an infectious agent may be suspected from clinical symptoms or laboratory findings that indicate an infection in a patient exposed to a medicinal product. This term applies only when a contamination of study treatment is suspected.

A12–5.3 REPORTING REQUIREMENTS FOR PREGNANCIES IN RO7247669 2100 mg ARM

A12–5.3.1 Pregnancies in Female Patients

Female patients of childbearing potential will be instructed through the Informed Consent Form to immediately inform the investigator if they become pregnant during the study or within 4 months after the final dose of RO7247669. A paper Clinical Trial Pregnancy Reporting Form should be completed and submitted to the Sponsor or its designee immediately (i.e., no more than 24 hours after learning of the pregnancy), either by faxing or by scanning and emailing the form using the fax number or email address provided to investigators. Pregnancy should not be recorded on the Adverse Event eCRF. The investigator should discontinue study treatment and counsel the patient, discussing the risks of the pregnancy and the possible effects on the fetus. Monitoring of the patient should continue until conclusion of the pregnancy. Any serious adverse events associated with the pregnancy (e.g., an event in the fetus, an event in the mother during or after the pregnancy, or a congenital anomaly/birth defect in the child) should be reported on the Adverse Event eCRF. In addition, the investigator will submit a Clinical Trial Pregnancy Reporting Form when updated information on the course and outcome of the pregnancy becomes available.

Attempts should be made to collect and report infant health information. When permitted by the site, an Authorization for the Use and Disclosure of Infant Health Information would need to be signed by one or both parents (as per local regulations) to allow for

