Appendix 12: Study Details Specific to RO7247669 2100 mg Arm

TABLE A12-4 SCHEDULE OF ACTIVITIES FOR RO7247669 2100 mg ARM (cont.)

- ^f After initiation of study treatment, all adverse events will be reported until 30 days after the final dose of study treatment or until initiation of new systemic anti-cancer therapy, whichever occurs first, and serious adverse events and adverse events of special interest will continue to be reported until 135 days after the final dose of study treatment or until initiation of new systemic anti-cancer therapy, whichever occurs first. After this period, all deaths, regardless of cause, should be reported. In addition, the Sponsor should be notified if the investigator becomes aware of any serious adverse event that is believed to be related to prior exposure to study treatment (see Section 5.6). *For details on reporting all treatment-related non-serious adverse events that lead to surgical delay, see Section 5.6.* The investigator should follow each adverse event until the event has resolved to baseline grade or better, the event is assessed as stable by the investigator, the patient is lost to follow-up, or the patient withdraws consent. Every effort should be made to follow all serious adverse events considered to be related to study treatment or trial-related procedures until a final outcome can be reported.

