Appendix 13: Study Details Specific to Atezo + Tira Arm

A13–5.2 ADVERSE EVENTS OF SPECIAL INTEREST FOR THE ATEZO + TIRA ARM (IMMEDIATELY REPORTABLE TO THE SPONSOR)

Adverse events of special interest are required to be reported by the investigator to the Sponsor immediately (i.e., no more than 24 hours after learning of the event; see Section 5.2.3 for reporting instructions). Adverse events of special interest for the Atezo + Tira arm are as follows:

- Cases of potential drug-induced liver injury that include an elevated ALT or AST in combination with either elevated bilirubin or clinical jaundice, as defined by Hy's Law (see Section 5.3.5.7)
- Suspected transmission of an infectious agent by the study treatment, as defined below:

Any organism, virus, or infectious particle (e.g., prion protein transmitting transmissible spongiform encephalopathy), pathogenic or non-pathogenic, is considered an infectious agent. A transmission of an infectious agent may be suspected from clinical symptoms or laboratory findings that indicate an infection in a patient exposed to a medicinal product. This term applies only when a contamination of study treatment is suspected.

- Pneumonitis
- Colitis
- Endocrinopathies: diabetes mellitus, pancreatitis, adrenal insufficiency, hyperthyroidism, and hypophysitis
- Hepatitis, including AST or ALT $> 10 \times$ upper limit of normal
- Systemic lupus erythematosus
- Neurological disorders: Guillain-Barré syndrome, myasthenic syndrome or myasthenia gravis, and meningoencephalitis
- Events suggestive of hypersensitivity, IRRs, cytokine-release syndrome, influenza-like illness, HLH, and MAS
- Nephritis
- Ocular toxicities (e.g., uveitis, retinitis, and optic neuritis)
- Myositis
- Myopathies, including rhabdomyolysis
- Grade ≥ 2 cardiac disorders (e.g., atrial fibrillation, myocarditis, pericarditis)
- Vasculitis
- Autoimmune hemolytic anemia
- Severe cutaneous reactions (e.g., Stevens-Johnson syndrome, dermatitis bullous, toxic epidermal necrolysis)

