Appendix 15: Study Details Specific to RO7247669 600 mg Arm

A15-5.2 ADVERSE EVENTS OF SPECIAL INTEREST FOR RO7247669 600 mg ARM (IMMEDIATELY REPORTABLE TO THE SPONSOR)

Adverse events of special interest are required to be reported by the investigator to the Sponsor immediately (i.e., no more than 24 hours after learning of the event; see Section 5.2.3 for reporting instructions). Adverse events of special interest for the RO7247669 600 mg arm are as follows:

- Cases of potential drug-induced liver injury that include an elevated ALT or AST in combination with either elevated bilirubin or clinical jaundice, as defined by Hy's Law (see Section 5.3.5.7)
- Suspected transmission of an infectious agent by the study treatment, as defined below:

Any organism, virus, or infectious particle (e.g., prion protein transmitting transmissible spongiform encephalopathy), pathogenic or non-pathogenic, is considered an infectious agent. A transmission of an infectious agent may be suspected from clinical symptoms or laboratory findings that indicate an infection in a patient exposed to a medicinal product. This term applies only when a contamination of study treatment is suspected.

A15-5.3 REPORTING REQUIREMENTS FOR PREGNANCIES IN RO7247669 600 mg ARM

A15-5.3.1 Pregnancies in Female Patients

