Appendix 16: Study Details Specific to RO7247669 600 mg+Tira Arm

A16-5.2 ADVERSE EVENTS OF SPECIAL INTEREST FOR THE RO7247669 600 mg+TIRA ARM (IMMEDIATELY REPORTABLE TO THE SPONSOR)

Adverse events of special interest are required to be reported by the investigator to the Sponsor immediately (i.e., no more than 24 hours after learning of the event; see Section 5.2.3 for reporting instructions). Adverse events of special interest for the RO7247669 600 mg+Tira arm are as follows:

- Cases of potential drug-induced liver injury that include an elevated ALT or AST in combination with either elevated bilirubin or clinical jaundice, as defined by Hy's Law (see Section 5.3.5.7)
- Suspected transmission of an infectious agent by the study treatment, as defined below:

Any organism, virus, or infectious particle (e.g., prion protein transmitting transmissible spongiform encephalopathy), pathogenic or non-pathogenic, is considered an infectious agent. A transmission of an infectious agent may be suspected from clinical symptoms or laboratory findings that indicate an infection in a patient exposed to a medicinal product. This term applies only when a contamination of study treatment is suspected.

- Pneumonitis
- Colitis
- Endocrinopathies: diabetes mellitus, pancreatitis, adrenal insufficiency, hyperthyroidism, and hypophysitis
- Hepatitis, including AST or ALT>10×ULN
- Systemic lupus erythematosus
- Neurological disorders: Guillain-Barré syndrome, myasthenic syndrome or myasthenia gravis, and meningoencephalitis
- Events suggestive of hypersensitivity, IRRs, cytokine-release syndrome, influenza-like illness, HLH, and MAS
- Nephritis
- Ocular toxicities (e.g., uveitis, retinitis, and optic neuritis)
- Myositis
- Myopathies, including rhabdomyolysis
- Grade≥2 cardiac disorders (e.g., atrial fibrillation, myocarditis, pericarditis)
- Vasculitis
- Autoimmune hemolytic anemia
- Severe cutaneous reactions (e.g., Stevens-Johnson syndrome, dermatitis bullous, or toxic epidermal necrolysis)

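### The AESI lists for both RO7247669 monotherapy arms omit the immune-mediated events that their own appendices say are listed there

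*Combined protocol and SAP*

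**What the plan says.** Section A12-5.1.1.3 of Appendix 12 (RO7247669 2100 mg) states: "In this study, specified immune-mediated adverse events will be considered adverse events of special interest and will be captured accordingly". It names Section A12-5.2 as the place for the list. That section introduces its content with "Adverse events of special interest for the RO7247669 2100 mg arm are as follows" and then gives two entries: potential drug-induced liver injury meeting Hy's Law, and suspected transmission of an infectious agent by study treatment.

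Appendix 15 (RO7247669 600 mg) has the same structure. Section A15-5.1.1.3 repeats the statement and points to Section A15-5.2, where "Adverse events of special interest for the RO7247669 600 mg arm are as follows" is followed by the same two entries.

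The combination arms differ. In Section A16-5.2, "Adverse events of special interest for the RO7247669 600 mg+Tira arm are as follows" introduces 17 entries, and Section A14-5.2 has the same 17. Section A13-5.2 (Atezo + Tira) has those 17 plus myelitis and facial paresis. All three include, for example, "Endocrinopathies: diabetes mellitus, pancreatitis, adrenal insufficiency, hyperthyroidism, and hypophysitis".

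AESI status has two consequences. Section A12-5.2 says "Adverse events of special interest are required to be reported by the investigator to the Sponsor immediately", meaning within 24 hours. Table A12-4, footnote f, says "all adverse events will be reported until 30 days after the final dose of study treatment", whereas "serious adverse events and adverse events of special interest will continue to be reported until 135 days after the final dose of study treatment". Both windows close earlier if new systemic anti-cancer therapy starts. The same footnote appears in Tables A13-6, A14-5, A15-4 and A16-5.

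**The concern.** The monotherapy appendices state an intention and then do not carry it out. Sections A12-5.1.1 and A15-5.1.1 name immune-mediated events among the potential risks of RO7247669, and the combination arms containing the same drug list them. The short lists therefore read as an omission rather than a deliberate choice.

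The AESI list decides what is collected after day 30 and what reaches the sponsor within 24 hours. At the same RO7247669 dose, the monotherapy arm and its tiragolumab counterpart work to different definitions. A raw AESI-rate comparison, or a comparison of late non-serious immune-mediated events, would then mix the difference in definition with any effect of tiragolumab.

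**Working it through.** The plan gives no figure to reproduce. The check is a count of list entries and calendar arithmetic on the reporting windows.

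**1. List entries.** Each list has two generic entries (Hy's Law, infectious agent); the rest are specific categories.

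| Arm | Section | Total | Generic | Specific |
|---|---|---|---|---|
| RO7247669 2100 mg | A12-5.2 | 2 | 2 | 0 |
| RO7247669 600 mg | A15-5.2 | 2 | 2 | 0 |
| RO7247669 2100 mg + Tira | A14-5.2 | 17 | 2 | 15 |
| RO7247669 600 mg + Tira | A16-5.2 | 17 | 2 | 15 |
| Atezo + Tira | A13-5.2 | 19 | 2 | 17 |

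**2. Windows.** Treatment is two 21-day cycles with dosing on Day 1 of each (Tables A12-1 and A15-1), so the planned last dose is on Day 1 + 21 = Day 22.

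- All adverse events: Day 22 + 30 = Day 52 (Week 8).
- Serious events and AESIs: Day 22 + 135 = Day 157 (Week 23).
- Difference: 135 − 30 = 105 days, and 105/135 = 78% of the longer window.

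**3. Visits in the gap.** Week 1 is taken to start on Day 1 and three months as 91 days.

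- Week 10 is Days 64 to 70, which is 42 to 48 days after the last dose.
- Week 13 is Days 85 to 91, which is 63 to 69 days after it.
- Surgery in Week 7 ± 7 days falls on Days 36 to 56. The first long-term follow-up is then on Days 127 to 147, which is 105 to 125 days after the last dose.

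All three visits fall between day 30 and day 135. Chemistry and thyroid tests are scheduled at Weeks 10 and 13 (Tables A12-4 and A15-4).

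**4. The same event in two arms.** Take non-serious hyperthyroidism with onset at Week 10. In the RO7247669 + Tira arms it is a listed endocrinopathy, reportable within 24 hours. In the monotherapy arms it is past the 30-day window, not serious and not listed, so it is not reportable. ALT or AST above 10 × ULN without raised bilirubin or jaundice is a second case: Sections A14-5.2 and A16-5.2 list it under hepatitis, but it does not meet the Hy's Law entry in A12-5.2 or A15-5.2.

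**5. Direction.** The monotherapy list is a subset of the combination list (2 of 17 entries). The difference in definition can therefore only lower a raw AESI count in the monotherapy arms relative to the combination arms.

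**The case against.** The best counter-argument is that the definition may sit elsewhere. Main-body Sections 5.2.3, 5.4.2 and 5.6 were not in the text available for this check, and a study-wide AESI list there cannot be excluded. In Appendix 11, the number A11-5.2.3 belongs to abortions, so A11-5.2 appears to be the pregnancy section. Yet Table A11-2, footnote f, still applies the 135-day AESI window to the control arm, so that arm's definition is probably held in text not seen. This limits what can be said about the control arm. It does not remove the contradiction: Sections A12-5.2 and A15-5.2 cite Section 5.2.3 for reporting instructions and present their two entries as the arm's AESIs, while A12-5.1.1.3 and A15-5.1.1.3 point to those same sections for the list.

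A second objection is that much remains captured, and this stands. All adverse events to 30 days, serious events to 135 days and Hy's Law cases are reportable. Later serious events believed related are notified, and reported events are followed until resolved or stable. Footnote f also refers to a separate rule in Section 5.6 for treatment-related non-serious events that delay surgery. A reader might infer that immune toxicity as a whole is under-captured in these arms; the documents do not support that.

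Two readings of size are also tempting. The 78% might be taken as a share of events, but it is a maximum of calendar time: new systemic anti-cancer therapy closes the window early in every arm. The AESI rates of 38.0% and 58.2% in Section A13-2.4 might be used to estimate the loss. They are total rates for tiragolumab plus atezolizumab in other studies, not rates of non-serious events on days 31 to 135 after two doses of RO7247669.

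**Conclusion.** The inconsistency is real in both monotherapy appendices and affects data collection. It should be fixed. Its scope is:

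- Non-serious immune-mediated events with onset 31 to 135 days after the last dose, or until new systemic anti-cancer therapy if earlier, are reportable in the tiragolumab arms but not in the RO7247669 monotherapy arms, apart from those covered by the Section 5.6 rule on surgical delay.
- Non-serious immune-mediated events in the monotherapy arms lose 24-hour notification at any time, unless they meet Hy's Law.

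The gap is at most 105 days per patient. The number of events lost cannot be computed: the documents give neither rate nor onset time for such late events, so the missed share could be anywhere from 0% to 100% of them. The calendar dates assume two doses on schedule; the day counts after the last dose do not.

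A reader might infer that every immune-mediated safety table, and the apparent added toxicity of tiragolumab, will be biased. That is conditional. The safety-analysis section was not available, and such tables may use a separate term grouping. The stopping rule stated in Section A14-2.6 uses treatment-related Grade ≥3 events, not AESIs. Only a raw AESI-rate comparison, or a comparison of late non-serious immune-mediated events, is clearly affected.

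**What to change.** Reconcile Section A12-5.1.1.3 with A12-5.2, and A15-5.1.1.3 with A15-5.2, by adding the immune-mediated categories to the two lists. The appendices do not say which events are meant, so the choice is the sponsor's; the list already in Sections A14-5.2 and A16-5.2 is the natural source. Before amending, check it against Sections 5.2.3 and 5.4.2 and the control-arm definition. The documents available do not justify imposing one AESI list on every arm, control included.

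Query treated monotherapy patients for listed non-serious events with onset on days 31 to 135 after the last dose. Re-collecting from first dose is largely unnecessary, because all events to day 30 after the last dose are already reportable. For any cross-arm AESI or immune-mediated table, state one common term list and apply it to every arm shown; Appendix 13 carries two entries that Appendices 14 and 16 do not.

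The cost is one amendment, a few more expedited reports and a limited retrospective query. Events not recorded at the time may be only partly recoverable, which favours acting early.
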